12.3. Serious Adverse Events (SAEs) and Serious Adverse Drug Reactions

Any SAE that occurs at any time during the study, including a clinically significantly abnormal laboratory test result that is considered serious, must be reported to Tonix or its designee(s) so that Tonix may comply with regulatory obligations. If the SAE is life-threatening or fatal, it must be reported to Tonix or its designee(s) immediately, by facsimile and telephone. For these and all other SAEs, an SAE report form must be completed and sent by facsimile or email to Tonix or its designee(s) within 1 working day of the site's initial awareness of the event. These requirements apply equally to all patients, regardless of the study phase or the at-risk patient's treatment assignment or dosage.

A serious adverse event (experience) or reaction is any untoward medical occurrence that, at any dose:

- Results in death,
- Is life-threatening,
- Requires in-patient hospitalization or prolongation of existing hospitalization,
- Results in persistent or significant disability/incapacity,
- Is a congenital anomaly/birth defect, or
- Is an important medical event

NOTE: The term "life-threatening" in the definition of "serious" refers to an event in which the patient was at risk of death at the time of the event. It does not refer to an event that hypothetically might have caused death if it were more severe.

Medical and scientific judgment should be exercised in deciding whether expedited reporting is appropriate in other situations, such as important medical events that may not be immediately life-threatening or result in death or hospitalization but may jeopardize the patient or may require intervention to prevent one of the other outcomes listed in the definition above. *These should also usually be considered serious.* Examples of such events are intensive treatment in an emergency room or at home for allergic bronchospasm, blood dyscrasias or convulsions that do not result in hospitalization, or development of drug dependency or drug abuse.

A death occurring during the study, during the per-protocol follow-up period, or reported to the Investigator after study participation (no required post-study time limit) must be reported to Tonix or its designee(s) immediately, whether or not it is considered treatment-related. Initial SAE reports must be followed by detailed descriptions. These should include copies of hospital

case records and other documents when requested. Telephone and e-mail reports must be confirmed promptly either by facsimile or by email. For reporting SAEs, one of Tonix’s designated medical monitors should be called.

The Investigator or other study personnel must immediately inform one of the Tonix Medical Monitors by phone or email of any AE considered serious or otherwise significant, as described above. **In addition, a completed SAE report form must be submitted to [REDACTED] within 24 hours of initial awareness of the event.**

Contact information for the Medical Monitors is provided below:

Table 3: Medical Monitoring Contact Information

[REDACTED]	[REDACTED]	[REDACTED]
[REDACTED]	[REDACTED]	[REDACTED]
[REDACTED]	[REDACTED]	[REDACTED]
[REDACTED]	[REDACTED]	[REDACTED]
[REDACTED]	[REDACTED]	[REDACTED]
[REDACTED]	[REDACTED]	[REDACTED]
[REDACTED]	[REDACTED]	[REDACTED]

For questions pertaining to the reporting of SAEs or the completion of SAE documentation, site personnel should call [REDACTED]

The investigator, or the sponsor or designee in the case of a central Institutional Review Board (IRB), also must notify the EC/IRB of the occurrence of the SAE, in writing, as soon as is practicable and in accordance with local law. A copy of this notification must be provided to Tonix or its designee.

In the event of an SAE that meets the criteria for expedited reporting, an Investigational New Drug (IND) Safety Report will be prepared for submission to the FDA.

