10.3. Visit 3 (Telephone Visit: Day 14)

Visit 3 will be done as a telephone call to the patient and should be conducted after 2 weeks of treatment, on Day 14 \pm 3 days.

The following steps should be completed:

- Assess changes in concomitant medications
- Assess study drug compliance based on patient verbal report
- Assess occurrence of adverse events, including any oral adverse events and whether an unscheduled visit is indicated for an examination of the oral cavity
- Review patient instructions regarding drug dosing.
- Administer the ‘Since Last Visit’ C-SSRS

After all of the items have been reviewed with the patient, the patient should be given an appointment to return to the clinic for Visit 4, and be re-instructed, as necessary, on dosing instructions, and reminded to bring study medication back to the clinic at their next visit.

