13.1. Populations for Analysis

The following populations will be defined for use in analyzing the efficacy and safety data in the study (see SAP for more details):

- Safety Population (SAFETY): All patients who receive at least 1 dose of study drug. All safety analyses and demographic/baseline characterization will be performed using this population, analyzed as treated, using the highest dose they were issued at any visit.
- Modified Intention-to-Treat Population (mITT): All randomized patients who have at least a baseline and one post-baseline CAPS-5 assessment. This is the primary population for efficacy analyses and patients will be analyzed based on their randomized treatment. See [Section 10.5.1](#) for early termination assessments.

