## 6. ANALYSIS POPULATIONS

The following analysis populations are planned for this study:

- **Safety Population (SAFETY):** All participants who receive at least 1 dose of study drug. Participants who are issued study drug, but return 100% of it (i.e., none consumed) will be excluded from the safety population; likewise participants that have no follow up following receipt of study drug to indicate they took drug are excluded. All safety analyses and demographic/baseline characterization will be performed using this population, analyzed as treated; participants will be summarized under TNX-102 SL 5.6 mg if they were issued it at any visit (including participants that are rolled over to open-label TNX-102 SL 5.6 mg in the case of an early stop recommended by the IDMC during the planned interim analysis).
- **Modified Intention-to-Treat Population (mITT):** All randomized participants who have at least a baseline and one post-baseline CAPS-5 assessment. This is the primary population for efficacy analyses and participants will be analyzed based on their randomized treatment.
- **Early Stop Safety Population (SAFETY):** This population is identical to the safety population but is limited to only the participants that are part of the interim analysis, (i.e. participants that are ongoing at the time of early stop are excluded). In the case of an early stop, safety results will be analyzed on both safety populations. Should the study continue to full enrollment (or full enrollment on an increased sample size), this population will not be utilized.
- **Early Stop Efficacy Population (mITT):** This population will be limited to those participants who are part of the interim analysis, i.e., among the approximately 275 patients defined as the population upon which the predefined interim analysis efficacy assessments will be conducted. Only those participants who have a baseline and at least one post-baseline CAPS-5 assessment will be evaluated for purposes of the interim analysis. Participants will be analyzed based on their randomized treatment. The dataset for this population will be defined by the completion or early termination of the last participant among this cohort.

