## **10. SAFETY AND TOLERABILITY ANALYSIS**

The safety analysis will be run on the Safety population. The analysis of safety assessments in this study will include summaries of the following safety and tolerability data collected for each participant:

- Adverse Events
- Clinical Laboratory Investigations
- C-SSRS
- Vital Signs
- Visual Examinations of Oral Cavity
- Electrocardiogram (ECG) Parameters (Obtained at Screening only)
- Assessment of Morning Sedation (via MTRSS)
- Changes from baseline in participant-rated CSFQ-14
- BDI-II

Summaries of continuous parameters will include raw values and change from baseline, as appropriate. Listings of safety data will also be presented.

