### **10.1.2 Serious Adverse Events**

A summary of incidence rates (frequencies and percentages) of SAEs by treatment group, SOC, and preferred term will be prepared for the Safety population. A data listing of SAEs will also be provided, displaying details of the event(s) captured on the CRF.

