### **10.1.3 Deaths**

A listing of deaths will also be provided for the Safety Population.

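### A death before the first scheduled contact, with dosing never established, could be left out of the SAP's death listing and SAE incidence table; listing deaths and SAEs for all randomized participants closes the gap

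*Protocol*

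**What the plan says.** **Reporting.** Protocol 12.3 covers "A death occurring during the study, during the per-protocol follow-up period, or reported to the Investigator after study participation" and says that such a death "must be reported to Tonix or its designee(s) immediately, whether or not it is considered treatment-related". It sets no time limit after the study and does not require confirmed dosing.

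**Population in the protocol.** Protocol 13.1 defines the Safety Population as "All patients who receive at least 1 dose of study drug" and refers to the SAP for more detail.

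**Population in the SAP.** SAP 6 keeps the one-dose definition and adds two exclusions. One is for participants who return all of their drug. The other reads "participants that have no follow up following receipt of study drug to indicate they took drug are excluded".

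**Outputs.** SAP 10 opens with "The safety analysis will be run on the Safety population". For SAEs, SAP 10.1.2 says "A summary of incidence rates (frequencies and percentages) of SAEs by treatment group, SOC, and preferred term will be prepared for the Safety population". For deaths, SAP 10.1.3 says "A listing of deaths will also be provided for the Safety Population". No other death listing is planned.

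**Timing.** Under Protocol 9.2 the first dose is self-administered at bedtime on Day 0. Under Protocol 10.3 the first scheduled contact after that is a telephone call, which "should be conducted after 2 weeks of treatment", with a window of 3 days either side of Day 14.

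**The concern.** The second exclusion in SAP 6 depends on something that happens after randomization, and death can be what prevents it. A participant who dies at home before anyone has asked about dosing may have no follow-up showing intake precisely because of the death. Membership of the safety population would then depend on the outcome that the population is used to describe.

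The first exclusion, for full return of drug, rests on positive evidence that no dose was taken. The second treats unknown intake as no intake. That runs against the SAP's habit elsewhere: SAP 7.3.1 counts an AE of missing severity as severe and one of missing relationship as related.

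Suicidal ideation and behavior is a named safety endpoint (Protocol 7.3.4), and patients leave Visit 2 with two bottles, 80 tablets in all (Protocol 9.1). An early death is the kind of event for which a reader would go to the death listing. Few or no deaths would be expected in a 12-week trial of this kind (an assumption; the documents give no figure), so one missing line could be the difference between one death and none.

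**Working it through.** The plan states no figure on this point, so there is nothing to reproduce. The check is to follow one case through the text.

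1. **Window without scheduled contact.** It starts at the first dose, on the evening of Day 0 (Protocol 9.2). It ends at the Visit 3 call on Day 14 ± 3 (Protocol 10.3): 14 − 3 = Day 11 at the earliest, 14 + 3 = Day 17 at the latest.

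2. **A death inside the window.** Protocol 12.3 makes it reportable at once. The sponsor holds the report.

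3. **Is the participant in the Safety Population?** SAP 6 asks whether any follow-up indicates that drug was taken. Three sources could answer:
   - the SAE report and the records requested with it (Protocol 12.3);
   - the CRF question on whether the event began before the first dose (SAP 7.3.1), where an answer of no implies a first dose;
   - a count of returned tablets (Protocol 9.5).

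   If any of these shows dosing, the participant stays in. If none does, the SAP 6 clause excludes the participant. SAP 7.3.1 gives no rule for an unknown answer to the CRF question, and neither document makes an exception for a participant who died.

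4. **What each planned output would then show.**

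| Output | Population in the text | Would the death appear? |
|---|---|---|
| Death listing (SAP 10.1.3) | Safety Population | No |
| SAE incidence table (SAP 10.1.2) | Safety Population | No |
| SAE data listing (SAP 10.1.2) | None in its own sentence; SAP 10 opening may govern | Unclear |
| AE data listings (SAP 10.1) | None in its own sentence; all AEs are to be shown | Unclear, possibly yes |
| Disposition (SAP 8.1) | Everyone with data in the database, with withdrawal reasons | Possibly, as a reason for withdrawal |
| Expedited reporting (Protocol 12.3) | All patients | Yes |

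5. **Scale.** With 275 planned per arm (Protocol 13.2), one death is 1/275 = 0.36%. This is the size of one omission, not the chance of one. The documents contain nothing from which that chance could be computed.

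**The case against.** The strongest reply is that a reported death generates its own follow-up. SAP 6 does not require a scheduled visit, only follow-up that indicates dosing. The SAE form, the detailed descriptions that must follow it, the CRF first-dose question and the tablet count are all such sources. In most cases one of them would settle the matter and the participant would be kept. This stands, and it narrows the gap to an early death for which all of these are silent. It does not remove the gap, because inclusion would then rest on case-by-case interpretation of the clause.

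It can also be said that the two documents do not conflict: Protocol 12.3 governs reporting, SAP 10 governs analysis, and Protocol 13.1 leaves the detail to the SAP. That is correct. The point is a gap in the planned outputs, not a contradiction.

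Several stronger readings are tempting, and the documents do not support them.

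- **That the death would vanish from every safety output.** The AE and SAE data listings name no population in their own sentences. The opening of SAP 10 can be read as covering them, but that is arguable.
- **That disposition would show only a withdrawal.** SAP 8.1 tabulates reasons, for everyone in the database.
- **That serious self-harm is exposed in the same way.** A survivor will usually produce an SAE report, an unscheduled visit or an early-termination visit. Protocol 10.5.1 has a procedure for withdrawal before Day 11 that includes collecting drug and assessing compliance.
- **That the size can be read from the calendar.** The window is 11/84 = 13.1% to 17/84 = 20.2% of the treatment period, but that is a share of time, not a probability of omission. An assumed 1–2% of 550 with no contact (5.5 to 11 participants) would describe ordinary loss to follow-up, not deaths.
- **That the Safety Population must be redefined.** Counting everyone with unknown intake as exposed would add people with no AE ascertainment and lower AE percentages. At the assumed 2%, the denominator would rise from 539 to 550, and 539/550 = 0.98. That is a trade-off, and the gap can be closed without it.

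**Conclusion.** The gap is real but narrow. As written, the SAP permits a death between the evening of Day 0 and the first contact to be left out of the death listing and the SAE incidence table when nothing establishes that a dose was taken, and the death can be the cause of that silence. The conclusion rests on reading the SAP 6 clause literally and on there being no exception for deaths, which neither document contains. It also supposes that the SAE report, the CRF question and the tablet count all fail to show dosing, which should be uncommon.

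The omission is possible, not certain; its probability cannot be derived from the documents, and its consequence is one missing line in a listing that may be very short. Efficacy results, AE rates and regulatory reporting are untouched. Severity is minor, and the change is worth making because it is cheap.

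**What to change.** In SAP 10.1.2 and 10.1.3, state that deaths and SAEs will be listed for all randomized participants. Each line should carry two flags: dosing status (confirmed, unknown or none) and membership of the Safety Population. Keep the SAE incidence table and all AE rates on the Safety Population as now defined in SAP 6, so that no denominator changes.

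The cost is one wider listing population and two flag variables. Any death or SAE in a participant outside the Safety Population would then be visible, with the reason for exclusion beside it.

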12.4. Pregnancy

The active pharmaceutical product in TNX-102 SL 2.8 mg tablets is cyclobenzaprine HCl, which is in Pregnancy Category B (See Appendix 3 for AMRIX® Package Insert). All pregnancies

occurring during the study (after exposure to study drug) or within 30 days after discontinuation of study drug must be followed until resolution (i.e., birth or voluntary or spontaneous termination of the pregnancy) and reported within 24 hours of the site's awareness to Tonix and/or its designee. Any patient found to be pregnant at any time during the study will be withdrawn from the study immediately. Any pregnancy outcome that meets the criteria for an SAE will be reported as an SAE.

13. STATISTICS

A full description of the statistical analyses to be performed at study completion will be provided in a Statistical Analysis Plan (SAP), which will be finalized prior to the interim analysis.

One interim analysis is planned (See [Section 13.6](#)) prior to the completion of the study. A full description of the interim analysis will be provided in an Interim Statistical Analysis Plan (ISAP), which will be finalized prior to the interim analysis.

Baseline will be defined as those values recorded closest to, but prior to administration of the first dose of study drug.

Unless otherwise noted, significance tests of treatment differences will be tested at the two-sided 0.05 level.

13.1. Populations for Analysis

The following populations will be defined for use in analyzing the efficacy and safety data in the study (see SAP for more details):

- Safety Population (SAFETY): All patients who receive at least 1 dose of study drug. All safety analyses and demographic/baseline characterization will be performed using this population, analyzed as treated, using the highest dose they were issued at any visit.
- Modified Intention-to-Treat Population (mITT): All randomized patients who have at least a baseline and one post-baseline CAPS-5 assessment. This is the primary population for efficacy analyses and patients will be analyzed based on their randomized treatment. See [Section 10.5.1](#) for early termination assessments.

13.2. Estimate of Sample Size

The study is planned to enroll approximately 550 patients total in a 1:1 randomization, that is, 275 patients in each of the placebo and TNX-102 SL 5.6 mg groups. [REDACTED]

13.3. Assessment of Demographic and Baseline Characteristics

Demographic and baseline characteristics such as age, gender, race/ethnicity, height, weight, BMI, presence of current major depressive episode, family status, education, employment status, and smoking history will be summarized by treatment group (TNX-102 SL and placebo) and overall using descriptive statistics.

Medical History will be coded using MedDRA and summarized by SOC and Preferred Term using frequency counts by treatment group.

13.4. Efficacy Analysis

13.4.1. Efficacy Endpoints

Primary Efficacy Endpoint:

The mean change from baseline (Visit 2) in the Total CAPS-5 score after 12 weeks of treatment evaluated at Visit 6.

Secondary Efficacy Endpoints: The first two secondary efficacy endpoints listed below are considered key secondary endpoints and will be tested in that order.

- CGI-I score (analyzed as a continuous variable) after 12 weeks of treatment.
- Change from baseline in the SDS total score after 12 weeks of treatment.

Other Secondary Efficacy Endpoints:

- Change from baseline in patients' quality of sleep using the PROMIS Sleep Disturbance scale after 12 weeks of treatment.
- Change from baseline in the disruption of work/school activities assessed using the SDS after 12 weeks of treatment.
- Change from baseline in disruption of social life/ leisure activities assessed using the SDS after 12 weeks of treatment.
- Change from Baseline in the disruption of family life/home responsibilities assessed using the SDS after 12 weeks of treatment.
- Change from baseline in CAPS-5 Arousal and Reactivity (Criterion E) score after 12 weeks of treatment.
- Change from baseline in CAPS-5 Intrusion symptoms (Criterion B) score after 12 weeks of treatment.
- Change from baseline in CAPS-5 Persistent Avoidance (Criterion C) score after 12 weeks of treatment.
- Change from baseline in CAPS-5 Negative Cognition and Mood (Criterion D) score after 12 weeks of treatment.
- Change from baseline in CAPS-5 Sleep Disturbance (item E-6) score after 12 weeks of treatment.

- Change from baseline in CAPS-5 Exaggerated Startle (item E-4) score after 12 weeks of treatment.
- PGIC score after 12 weeks of treatment.
- Proportion of patients with a PGIC score of “much improved” or “very much improved” after 12 weeks of treatment
- Proportion of patients with a treatment response on the CGI-I defined as a CGI-I score of “much improved” or “very much improved” after 12 weeks of treatment.
- Proportion of patients with a Total CAPS-5 score of 0 –10 (asymptomatic/few symptoms) after 12 weeks of treatment.
- Proportion of patients with a Total CAPS-5 score of 0 -22 (asymptomatic or mild PTSD/subthreshold) after 12 weeks of treatment.
- Proportion of patients with Response, defined as a ≥ 10 -point improvement from baseline in Total CAPS-5 score after 12 weeks of treatment.
- Proportion of patients with Loss of Diagnosis, defined as Response AND no longer meeting DSM-5 symptom criteria in any one or more of the four clusters (B, C, D, E) after 12 weeks of treatment.
- Proportion of patients in Remission, defined as Loss of Diagnosis AND Total CAPS-5 score ≤ 10 after 12 weeks of treatment.
- Proportion of patients achieving sustained Remission, defined as Loss of Diagnosis AND Total CAPS-5 score ≤ 10 after 8 weeks AND 12 weeks of treatment.
- Proportion of patients with a $\geq 50\%$ improvement from baseline in Total CAPS-5 score after 12 weeks of treatment.
- Change from baseline in BDI-II score after 12 weeks of treatment.
- Change from baseline in CAPS-5 Reckless or Self-Destructive Behavior (item E-2) score after 12 weeks of treatment.

Exploratory Endpoints: Any exploratory endpoints will be delineated in the SAP.

13.4.2. Primary Efficacy Analysis

The primary efficacy analysis will use a mixed model repeated measures (MMRM) approach to estimate mean change from baseline in the Total CAPS-5 score evaluated after 12 weeks of treatment in the TNX-102 SL 5.6 mg and placebo arms. The model will include all patients in the mITT population, and the dependent variable will be the observed change from baseline in total CAPS-5 score at each post-randomization visit. Covariates in the model will include the fixed categorical effects of treatment, site, sex, current tobacco use status, presence of current MDE, visit and treatment by visit interaction, as well as the continuous fixed covariates of baseline score and baseline score by visit interaction. Missing data will be imputed via multiple imputation (MI), and details regarding the MI approach will be described in the SAP.

The primary analysis will be followed by several sensitivity analyses. Further details on sensitivity analyses can be found in the SAP.

